## **F STUDY METHODS**

### **F.1 Point of enrollment**

Patients will be pre-screened for potential enrollment in the clinical study based on prior medical history and records of office SBP. A pre-screening log will be maintained to determine the number of patients that do not meet study eligibility criteria and who will not be approached for participation in the study.

A subject is considered enrolled in this clinical study at the time at which the subject and investigator or authorized designee have personally signed and dated the Patient Information and Informed Consent Form. Written consent must have been obtained prior to Screening Visit 1 (SV1).

Investigational sites will maintain a subject identification log. However, this document will not be submitted to the sponsor.

A schedule outlining protocol required visits and assessments for subjects enrolled in the study is displayed in Table 4. A flowchart depicting the study design overview is provided in

Figure 12. The following procedures will be followed for all subjects, excluding crossovers, enrolled in this study until study exit.

[figure not shown]

Figure 12: Study Design Overview

## F.2 Screening Visit 1

After confirmation that the investigator or authorized designee and subject have personally signed and dated Patient Information and Informed Consent Form, the following assessments will be performed at Screening Visit 1:

- a) **Medical History** will be documented from the study subject to evaluate for prior or existing medical conditions and/or procedures that would exclude subjects from participation in the study.
- b) **Office Blood Pressure** measurements will be obtained in accordance with Appendix L.7. This blood pressure measurement will not be used as the baseline BP measurement but will be used, in conjunction with the subject's medical history, to determine if, in the investigator's judgment, the subject's BP at Screening Visit 2 will qualify for inclusion in the study following the antihypertensive drug washout period. However, if the subject's SBP is  $\geq 180$  mmHg, the subject will be excluded at Screening Visit 1.
- c) **Medication & Adverse Event Reviews** will be completed to document baseline medication use and adverse events that occur after enrollment.

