### F.7 Follow-Up Procedures

Subjects will return for in-office follow-up visits at week 2, 4 and 8 ( $\pm 3$  days) post-procedure. A phone call follow-up will be conducted at week 6 and 10 ( $\pm 3$  days) post-procedure. There will additionally be follow-up visits at 3 and 6 months ( $\pm 14$  days) post-procedure. Upon completion of the 3 month follow-up visit, a Medication Re-Introduction protocol to resume antihypertensive medications must be followed, if required. See instructions in Section F.9 for Medication Re-Introduction for Subjects with Systolic OBP  $\geq 140$  mmHg at 3M follow-up visit. Subjects will then return at 6 months ( $\pm 14$  days), 12, 24, and 36 months post-procedure with visits conducted  $\pm 30$  days, from the procedure date. In case of a crossover, subjects will return for in-office visits at 1, 3, 6, 12 and 24 months post-crossover procedure.

Alternative methods of data collection may be necessary in the case of extenuating circumstances, such as a global pandemic, when subjects are prohibited from coming into the office for required assessments. For all assessments completed via alternative methods in these circumstances, sites are not required to enter a protocol deviation for missing, and/or alternative data collection. Data unable to be collected remotely or via an alternative method should be collected at the next possible in-person visit. In the event a subject is unable to return for an in-office follow-up visit, the alternative methods of obtaining follow-up assessments are listed below:

- In-home visit by trained and delegated site personnel or designee, i.e. home health care personnel. The following assessments may not be completed with an in-home visit:
  - Renal Artery Imaging:
    - Make every effort to schedule in-person renal artery imaging as soon as possible.
    - When possible, the subjects may be referred to a local imaging center for assessment. Local imaging technicians would require study training and delegation prior to assessment.

In the event an in-home visit is not possible, the alternate methods for obtaining follow-up assessments are listed below:

- Virtual Visit, i.e. inclusive of video with study subject. The following assessments may not be completed with a virtual visit:
  - Clinical Assessment, limited review to be completed per physician discretion.
  - Laboratory Tests:

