    - When possible, the subject should be referred to a local laboratory to collect samples. Laboratory Kits to be provided to subjects in advance of the visit by the study site.
  - Renal Artery Imaging:
    - Make every effort to scheduled in-person renal artery imaging as soon as possible.
    - When possible, subjects may be referred to a local imaging center for assessment. Local imaging technicians would require study training and delegation prior to assessment.
  - Office Blood Pressure and ABPM measurements may be collected and designated as subject-reported in the case report form.
    - Office blood pressure and ABPM units to be provided to the subjects in advance of the visit by the study site.
  - Witnessed pill intake prior to ABPM.
    - Documentation of pill intake will be assessed virtually.
- Phone Visit, i.e. no video with the subject. The following assessments may not be completed with a phone visit:
  - Clinical Assessment, limited review to be completed per physician discretion.
  - Laboratory Tests:
    - When possible, the subject should be referred to a local laboratory to collect samples. Kits to be provided to subjects in advance of the visit by study site.
  - Renal Artery Imaging:
    - Make every effort to schedule in-person renal artery imaging as soon as possible.
    - When possible, the subjects could be referred to a local imaging center for assessment. Local imaging technicians would require study training and delegation prior to assessment.
  - Office Blood Pressure and ABPM measurements may be collected and designated as subject-reported in the case report form.
    - Office blood pressure and ABPM units to be provided to the subjects in advance of the visit by study site.
  - Witnessed pill intake prior to ABPM.

- Documentation of pill intake will be assessed over the phone as confirmed verbally by subject.

In case the Symplicity Spyral™ catheter and Symplicity G3™ generator receive commercial approval in the United States, Canada and/or Japan during the course of this clinical study, the follow-up assessments will continue to be conducted as planned unless otherwise instructed.

Follow-up procedures for all subjects are listed below. Follow-up procedures must be performed by blinded site personnel through 6 months follow-up for each subject.

- a) **EQ-5D:** The Euro-Qol 5D (EQ-5D) will be administered at the 3, 6, 12, 24 and 36 month post-procedure visits to measure health outcomes.

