**Table 8: Adverse Event Reporting Requirements**

|        |   |
|--------|---|
| EC/IRB | Submit to EC/IRB per local reporting requirement. |
|--------|---|

*F.16.5 Data Safety Monitoring Board and Clinical Events Committee*

A Data Safety Monitoring Board (DSMB) will be established to monitor the health, safety and welfare of patients. Additionally, a Clinical Events Committee (CEC) will be established to adjudicate any safety endpoint events. See Section 1.2 Advisory Committees.

*F.16.6 Emergency contact details in case of serious AEs*

In the case a Serious Adverse Event or Serious Adverse Device Effect occurs and requires immediate consultation, the investigators can contact the sponsor (or designee) as outlined in the Investigator Site File.

**F.17 Subject accountability***F.17.1 Missed Follow-up Visits*

Every effort should be made to ensure subjects return to the investigational site for all protocol required follow-up visits. If the subject is unable to complete an in-office, in-home, virtual, or phone visit, the Investigator (or designee) must document the reason the subject was unable to complete the visit and, if applicable, follow the requirements for deviation reporting as outlined in section F.17. If a subject misses a follow-up visit, they will not be considered lost to follow up and all remaining follow-up visits will be scheduled per protocol. The Investigator should also make every effort to contact the subject within the visit window, to collect the subject's vital status as well as information related to potential adverse events.

At a minimum, four attempts must be made to contact the subject and documented in the subject's study records before a visit can become a missed visit:

- 3 telephone attempts to the subject's last known phone number, and if unsuccessful,
- 1 letter from the PI to the subject's last known address sent by courier with tracking information.

*F.17.2 Unscheduled Follow-up Visits*

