All the safety endpoints will be adjudicated by the Clinical Events Committee (CEC). The following algorithm will be used to evaluate the safety event rates: The denominator will include all subjects who either had a CEC adjudicated event prior to the time of interest (180 days for 6 months events, for example), or had last contact date that is beyond the lower window of the follow up (166 days for 6 month events, for example). The numerator will include all subjects who had CEC adjudicated events up to the time of interest (180 days for 6 months events, for example).

The secondary safety endpoints, out to 6-months follow-up, will be compared between treatment groups using Fisher's exact test. Two-sided 95% confidence intervals of the difference between treatment groups will also be presented.

After 6-months follow-up, control subjects may crossover (undergo renal denervation), and secondary safety endpoints will be summarized by group (RDN, Crossovers, Non-Crossovers). RDN vs. Crossover vs. Non-Crossover groups will be compared out to 36 months post-procedure for the RDN and Non-Crossover groups and out to 24 months for the Crossover group using chi-square tests for categorical data and ANOVA for continuous data.

The secondary safety analyses will be performed using the ITT population defined in section 9.1.3.1.

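### The two creatinine-based safety rates count a contacted but untested subject as event-free, and the protocol conflicts on testing escape subjects and on reporting renal events after month 12

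*SAP*

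**What the plan says.** SAP 9.9.2 and Protocol H.3 use one rule for all safety rates. The denominator takes a subject who had an adjudicated event before the time point "or had last contact date that is beyond the lower window of the follow up". For the other half of the fraction, "The numerator will include all subjects who had CEC adjudicated events" up to the time point. The rule covers the eGFR-decline and creatinine-rise endpoints at 1 month and at 3, 6, 12, 24 and 36 months. "The secondary safety endpoints, out to 6-months follow-up, will be compared between treatment groups"; after that, RDN, Crossover and Non-Crossover groups are shown. SAP 9.4 deals with missing data for the two powered efficacy endpoints only.

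The protocol foresees contact without a blood test:

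- **Missed visits (F.17.1).** "The Investigator should also make every effort to contact the subject within the visit window", for vital status and adverse events.
- **Remote visits (F.7).** "In the event an in-home visit is not possible, the alternate methods for obtaining follow-up assessments are listed below", namely virtual and phone visits. "The following assessments may not be completed with a phone visit" introduces a list that includes laboratory tests, and the virtual-visit list does the same. F.7 also provides for referral to a local laboratory when possible, with kits sent ahead, and data not obtained remotely "should be collected at the next possible in-person visit".
- **Escape subjects.** SAP 9.1.3.1 keeps them in ITT. F.8 moves them to Table 6 (Table 3 in the Synopsis), which has no Chem-7 row. Yet F.1 states: "The following procedures will be followed for all subjects, excluding crossovers, enrolled in this study until study exit". The F.7 list includes Chem-7, and F.11 has creatinine assessed for the whole study. None of the three states an escape exception. F.8 also sends subjects restarted for a safety concern to Table 8, which is the adverse event reporting table.

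After month 12, F.11 makes a confirmed rise a reportable adverse event without a time limit, while F.7(g) and F.16.2 restrict reporting to serious adverse events.

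**The concern.** A contact-based denominator suits death or stroke, because a subject reached by phone can be asked about them. It does not suit an endpoint that only a blood test can show. For the two renal endpoints the reported rate mixes subjects tested and normal with subjects not tested, and no output named in the SAP separates them. The disposition table counts completed visits, and F.7 waives the deviation entry for data missing under alternative methods. Renal function is a real safety question for a device that ablates in the renal arteries, and a low or zero rate is likely to be cited as reassurance. The post-12-month conflict touches the numerator of the same endpoints at 24 and 36 months.

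**Working it through.** **1. The plan's own figure.** The 6-month visit is at 180 ± 14 days: 180 − 14 = 166 days, the lower limit used in the rule. It reproduces.

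**2. How the rule classifies a subject at a time point.**

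| Earlier adjudicated event | Contact past lower window | Creatinine in or after window | Counted as |
|---|---|---|---|
| Yes | either | either | event |
| No | Yes | Yes, no event | event-free |
| No | Yes | None | event-free |
| No | No | None | excluded |

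The third row is the problem.

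**3. Both endpoints rest on one measurement.** At constant age, a 40% eGFR fall needs a creatinine ratio of 0.6^(−1/1.154) = 1.557 under MDRD, or 0.6^(−1/1.094) = 1.595 under the Japanese formula. Every such fall also passes F.11's 50% trigger, and neither can be seen without a draw.

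**4. Scheduled post-procedure Chem-7.** Table 4 has seven draws: discharge, week 4, and months 3, 6, 12, 24 and 36. Tables 3/6 have none. Escape happens at or before the 3-month visit, so at least the four draws from month 6 on have no row for these subjects. F.8 asks for a best-effort Chem-7 before medication is restarted. The number of escape subjects is not given.

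**5. Zero-event illustration.** The two-sided exact 95% upper bound for 0/n is 1 − 0.025^(1/n). The 166 RDN subjects are from Protocol B.1.2; 15% untested is an assumption (166 × 0.85 ≈ 141).

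- 1 − 0.025^(1/166) = 2.20%
- 1 − 0.025^(1/141) = 2.58%

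**6. Size if events occur.** Let u be the share of true events never found at any draw or by any other route up to the time point. Reported rate = true rate × (1 − u). Neither input is in the documents. Assuming a true rate of 3%, or 166 × 0.03 = 4.98 events:

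- u = 2%: 2.94%, 0.10 events lost
- u = 15%: 2.55%, 0.75 events lost

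**7. How alternative rules behave.** Assume 166 subjects, 5 true events (3.01%), 15% untested after month 6, and the same risk in tested and untested subjects. Month-12 rate:

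| Rule | All events early | Half early | All late |
|---|---|---|---|
| Contact-based | 5/166 = 3.01% | 4.625/166 = 2.79% | 4.25/166 = 2.56% |
| Event, or creatinine in or after window | 5/142 = 3.52% | 4.625/141.48 = 3.27% | 4.25/141 = 3.01% |
| Time to first event, censored at last creatinine | 3.01% | 3.01% | 3.01% |

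Late events found: 5 × 141/166 = 4.25. Half early: 2.5 + 2.5 × 0.85 = 4.625 found, with 163.5 × 0.85 = 138.98 tested later and 2.5 + 138.98 = 141.48 in the second denominator. Time to event, half early: 1 − (1 − 2.5/166)(1 − 2.125/138.98) = 3.01%.

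The contact rule is exact when events are early and low when they are late. The creatinine-based proportion is exact when events are late and high when they are early. Showing both brackets the answer under these assumptions.

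**The case against.** Much of the case on the other side stands, and it rules out several stronger readings.

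- *That remote visits mean no creatinine.* F.7 offers in-home visits first (they exclude only imaging), then local-laboratory referral and later catch-up. Remote visits are also unlikely to touch the 1- and 3-month rates of the 331 subjects whose 3-month data were presented in March 2020.
- *That the rate is diluted by the whole untested share* (for example 5/166 = 3.01% becoming 5/141 = 3.55%). The numerator is cumulative, remaining visits stay scheduled after a missed one, and a sustained rise can be found at a later draw, though perhaps credited to a later time point. Protocol B.1.2 also reports no creatinine rise above 50% through 3 months in the first 80 subjects.
- *That renal events after month 12 are lost.* Some confirmed rises qualify as serious. F.11 records the confirmatory draw on its own form, and I.2.3 has the sponsor's safety department identify events for the CEC, a route not expressly limited to events filed by sites.
- *That the escape schedule is plainly an error.* Tables 3/6 also lack rows for ABPM, clinical assessment and drug testing, so an intended branch is plausible. The Table 8 reference is probably a cross-reference slip.

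The CEC Charter and the table specifications, which now hold the lab-value algorithms, may contain a safeguard. Neither is among the documents.

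What remains is that neither the SAP nor the protocol requires a creatinine value for these two rates. Even if the escape branch is intended, it leaves subjects without scheduled tests in the denominator, and F.7 and F.11 do not acknowledge it.

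**Conclusion.** The rule is unsuited to these two endpoints, and the plan as written can produce untested subjects who count as event-free. The two conflicts, on Chem-7 for escape subjects and on reporting after month 12, are in the text. The size is unknown and probably small: under one event in 166 on the assumed inputs (true rate 3%, u up to 15%), and a zero-event upper bound moving from 2.20% to 2.58% if 25 of 166 were untested. No size is claimed for the post-12-month conflict.

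A reader might infer that the rule favours denervation or weakens the primary safety result. The documents support neither. The untested share by group is not given, so the direction is unknown. The randomised comparison ends at 6 months. The two endpoints are unpowered and are not components of the MAE composite. The change is worth making because it is cheap and lets a reader see how much testing lies behind each rate.

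**What to change.** 1. In SAP 9.9.2 and Protocol H.3, for these two endpoints only, report by group and visit the number with and without an evaluable creatinine. Beside the contact-based rate, show a rate whose denominator is an adjudicated event, or an evaluable creatinine in or after the window. Note that it can overstate when events are found early and event-free subjects are later untested. A time-to-first-event estimate censored at the last creatinine may be added as a sensitivity analysis. It assumes that missing draws are unrelated to renal outcome, which is least credible for escape subjects.
2. Screen the Chem-7 results already collected for both thresholds and refer crossings to the CEC, so that the endpoints stay adjudicated.
3. Reconcile F.11 with F.7(g), F.16.2 and Tables 1/4 on reporting after month 12.
4. Reconcile Tables 3/6 with F.7 and F.11 on Chem-7 for escape subjects, and correct F.8's reference to Table 8. No clinical schedule is proposed here.

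The cost is some SAP wording, some programming on existing data, and smaller denominators at later visits. Values never drawn cannot be recovered, only reported as missing.

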- **Enrollment (consent) to 12-months post procedure:** all medications and all adverse events
  - **12 to 36 months post-procedure:** all medications and serious adverse events only. Previously reported adverse events will be followed up through resolution until the end of the study.
- h) **Renal Artery Imaging** will be performed at the 6-month post-procedure visit to assess if a renal artery stenosis is suspected. A renal duplex ultrasound (DUS) will be obtained at 6M and submitted to the DUS Core Laboratory. If the DUS is determined to be nondiagnostic a repeat DUS, a MRA, CT or angiogram will be performed (repeat imaging is recommended to be completed within 30 days after confirmation of non-diagnostic imaging). If evidence of a clinically significant stenosis is indicated by the DUS or MRA/CT Core Laboratories, an angiogram must be obtained and submitted to the Angiographic Core Laboratory.
- A renal duplex ultrasound (DUS) at 6-month follow-up is not required for subjects randomized to the control group who are crossing over, if they are having the renal denervation procedure done within 30 days of their 6 month follow-up visit. If they are not having the renal denervation procedure done within the 30 days of their 6 month follow-up visit, a renal duplex ultrasound (DUS) is required.
  - The 12-month renal imaging will be required for all randomized subjects. If the renal imaging is determined to be nondiagnostic, a repeat DUS, MRA, CTA or angiogram will be performed. If repeat DUS, CTA, or MRA is nondiagnostic or evidence of a clinically significant stenosis ( $>60$ - $70\%$ ) is indicated, an angiogram must be obtained and submitted to the Angiographic Core Laboratory. Subjects who have already completed their 12-month visit follow up at the time of protocol approval will be required to undergo renal imaging at their next scheduled follow-up visit unless they have a renal angiogram due to crossover. For participating sites in Germany and the UK, only DUS or renal MRA imaging at the 12-month follow-up visit (or 24M or 36M follow-up as applicable) will be performed. For these countries, if the initial DUS or initial renal MRA is non-diagnostic, a repeat DUS or repeat renal MRA should be performed. If the initial imaging modality or subsequent repeat(s) are non-diagnostic, the investigator should choose the repeat imaging modality (DUS or MRA) that is expected to yield the required information for a diagnostic study.

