All the safety endpoints will be adjudicated by the Clinical Events Committee (CEC). The following algorithm will be used to evaluate the safety event rates: The denominator will include all subjects who either had a CEC adjudicated event prior to the time of interest (180 days for 6 months events, for example), or had last contact date that is beyond the lower window of the follow up (166 days for 6 month events, for example). The numerator will include all subjects who had CEC adjudicated events up to the time of interest (180 days for 6 months events, for example). The secondary safety endpoints will be compared between treatment groups using Fisher's exact test. In addition, two-sided 95% confidence intervals of the difference between treatment groups will be presented. The secondary safety analyses will be performed using the ITT population defined in H1.

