#### **Secondary Safety Endpoints**

Acute/Procedural Safety Secondary Endpoints - Compared Between Groups at 1 Month Post-Procedure:

- Significant embolic event resulting in end-organ damage
- Renal artery perforation requiring intervention
- Renal artery dissection requiring intervention
- Vascular complications
- End-Stage Renal Disease
- ≥40% decline in eGFR
- New Myocardial Infarction
- New Stroke
- Renal artery re-intervention
- Major bleeding according to TIMI definition (i.e. intracranial hemorrhage, ≥5g/dl decrease in hemoglobin concentration, a ≥15% absolute decrease in hematocrit, or death due to bleeding within 7 days of the procedure)
- Increase in serum creatinine > 50% from Screening Visit 2
- New renal artery stenosis > 70%, confirmed by angiography and as determined by the angiographic core laboratory
- Hospitalization for hypertensive crisis not related to confirmed non-adherence with medications or the protocol

Chronic Safety Secondary Endpoints – Compared Between Groups at 3, 6, 12, 24, and 36 Months Post-Randomization:

- Composite Safety Endpoint, defined as a composite of the following events:
  - All-cause mortality
  - End-Stage Renal Disease (ESRD)
  - Significant embolic event resulting in end-organ damage
  - Renal artery perforation requiring intervention
  - o Renal artery dissection requiring intervention
  - Vascular complications
  - Hospitalization for hypertensive crisis not related to confirmed non-adherence with medications and/or the protocol.
  - New renal artery stenosis > 70%, confirmed by angiography and as determined by the angiographic core laboratory
- All-cause mortality
- End-Stage Renal Disease
- ≥40% decline in eGFR
- New Myocardial Infarction
- New Stroke

- Renal artery re-intervention
- Major bleeding according to TIMI definition (i.e. intracranial hemorrhage, ≥5g/dl decrease in hemoglobin concentration, a ≥15% absolute decrease in hematocrit, or death due to bleeding within 7 days of the procedure)
- Increase in serum creatinine > 50% from Screening Visit 2
- New Renal artery stenosis >70%, confirmed by angiography and as determined by the angiographic core laboratory
- Hospitalization for hypertensive crisis not related to confirmed non-adherence with medications or the protocol

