#### 9.9.2. Secondary Safety Objectives

The following secondary safety endpoints will be assessed:

 Acute/Procedural Safety Secondary Endpoints – Compared Between Groups at 1 Month Post-Procedure:

- Significant embolic event resulting in end-organ damage
- Renal artery perforation requiring intervention
- Renal artery dissection requiring intervention
- Vascular complications
- End-Stage Renal Disease
- ≥40% decline in eGFR
- New myocardial infarction
- New stroke
- Renal artery re-intervention
- Major bleeding according to TIMI definition (i.e. intracranial hemorrhage, ≥5g/dl decrease in hemoglobin concentration, a ≥15% absolute decrease in hematocrit, or death due to bleeding within 7 days of the procedure)
- Increase in serum creatinine >50% from Screening Visit 2
- New renal artery stenosis >70%, confirmed by angiography and as determined by the angiographic core laboratory
- Hospitalization for hypertensive crisis not related to confirmed non-adherence with medications or the protocol
- Chronic Safety Secondary Endpoints Compared Between Groups at 3, 6, 12, 24, and 36 Months Post- Randomization:
  - Composite Safety Endpoint, defined as a composite of the following events:
    - All-cause mortality
    - End-Stage Renal Disease (ESRD)
    - Significant embolic event resulting in end-organ damage
    - Renal artery perforation requiring intervention
    - Renal artery dissection requiring intervention
    - Vascular complications
    - Hospitalization for hypertensive crisis not related to confirmed non-adherence with medications and/or the protocol
    - New renal artery stenosis >70%, confirmed by angiography and as determined by the angiographic core laboratory
  - ≥ 40% decline in eGFR
  - Increase in serum creatinine >50% from Screening Visit 2
  - New myocardial infarction
  - New stroke
  - Renal artery re-intervention
  - Major bleeding according to TIMI definition (i.e. intracranial hemorrhage, ≥5g/dl decrease in hemoglobin concentration, a ≥15% absolute decrease in hematocrit, or death due to bleeding within 7 days of the procedure)
  - Hospitalization for hypertensive crisis not related to confirmed non-adherence with medication and/or protocol.
  - Summary of health related Quality of Life (HRQoL) analysis based on reporting measures using accepted QoL instruments (EQ5D and SF36).

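### The safety-rate denominator requires only a late enough contact, so for renal artery stenosis a subject without a diagnostic scan counts as event-free

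*SAP*

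**What the plan says.** SAP 9.9.2 gives a single algorithm for all safety event rates. A subject enters the denominator with an adjudicated event before the time of interest, or if the subject "had last contact date that is beyond the lower window of the follow up". Protocol H.3 has the same rule ("or had last contact date that is beyond the lower window of the follow up"). The numerator holds adjudicated events up to the time of interest. The worked example is 6 months: day 180 for events, day 166 for contact.

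The stenosis item is "New renal artery stenosis > 70%, confirmed by angiography and as determined by the angiographic core laboratory" in SAP 5.2. In SAP 9.9.2 it recurs among the acute items and, for the later time points, inside the composite: "New renal artery stenosis >70%, confirmed by angiography and as determined by the angiographic core laboratory".

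Protocol F.7 requires renal imaging at 6 months (ultrasound first) and at 12 months for all randomized subjects. Under the general 12-month rule, if the repeat scan is non-diagnostic or significant stenosis is indicated, "an angiogram must be obtained and submitted to the Angiographic Core Laboratory". For Germany and the UK only ultrasound or MRA is foreseen at 12 months (or at 24 or 36 months where applicable). If these stay non-diagnostic, "the investigator should choose the repeat imaging modality (DUS or MRA) that is expected to yield the required information for a diagnostic study". The footnotes to Protocol Tables 1, 3, 4 and 6 repeat this.

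SAP 9.9.2.1 plans a descriptive 12-month stenosis rate with an exact confidence interval and does not name its denominator. SAP 9.9.9 announces long-term imaging analyses without further content.

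**The concern.** Contact is a fair basis for death, myocardial infarction or stroke, because contact usually reveals them. Stenosis is different: the plan looks for it by scheduled imaging, so a subject who was reached but not diagnostically scanned has not been assessed. Under the stated rule that subject still adds one to the denominator and cannot add to the numerator unless an angiogram is done for some other reason.

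Protocol J.2 lists stenosis from radiofrequency energy as a possible risk of the therapy, so this is a device-specific safety question. No planned table clearly shows how many subjects in the denominator were scanned. The disposition table in SAP 9.1.1 counts visits, not scans. The COVID-19 deviation tables in SAP 9.12 cannot be relied on to fill the gap, because in such circumstances "sites are not required to enter a protocol deviation for missing, and/or alternative data collection" (Protocol F.7).

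**Working it through.** **1. The plan's own figure.** SAP 9.9.2.1 gives (0.6%, 8.5%) for 3 events in 100. The exact (Clopper-Pearson) limits are the 2.5% quantile of Beta(3, 98) and the 97.5% quantile of Beta(4, 97), that is 0.62% and 8.52%. The figure reproduces. It describes 100 subjects whose stenosis status is known.

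**2. One subject through the rule.** The 12-month window is days 330 to 390 (Protocol Table 1). Take a subject reached by phone on day 345 and not scanned. Contact is past day 330, so the subject is in the 12-month denominator. Without an angiogram there is no event. If a make-up scan on day 400 leads to a confirmed stenosis, that event falls after the nominal 12-month day (360) and does not change the 12-month row.

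**3. Where the plan produces such subjects.**
- Remote visits. For a phone visit, "The following assessments may not be completed with a phone visit", and renal imaging is on that list; it is also listed for in-home and virtual visits. The scan is to be made up later.
- Subjects already past their 12-month visit when the imaging requirement was approved. They are scanned at the next scheduled visit, unless a crossover angiogram was done, but their 12-month contact counts.
- German and UK subjects whose repeat ultrasound or MRA scans all stay non-diagnostic. No angiogram step is stated for them.
- At 6 months, a missed ultrasound has the same effect in any country.

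**4. Size of the dilution.** Let u be the share of contacted subjects without a diagnostic scan. The documents do not give u; 5% to 30% is assumed. With equal risk in scanned and unscanned subjects, and no stenosis found without a scan:

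shown rate = true rate × (1 − u)

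The table uses the plan's 3.1%. Its right-hand columns take 3 events among 100 contacted subjects and count only the scanned ones.

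| u | 3.1% is shown as | events / scanned | exact 95% interval |
|---|---|---|---|
| 0 | 3.1% | 3/100 = 3.0% | 0.6% to 8.5% |
| 5% | 2.9% | 3/95 = 3.2% | 0.7% to 9.0% |
| 10% | 2.8% | 3/90 = 3.3% | 0.7% to 9.4% |
| 20% | 2.5% | 3/80 = 3.8% | 0.8% to 10.6% |
| 30% | 2.2% | 3/70 = 4.3% | 0.9% to 12.0% |

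If some stenoses were already confirmed at 6 months, the loss shrinks. With a share f still to be found, shown = 3.1% × (1 − u × f). At f = 0.5 (assumed) this gives 3.1% × 0.975 = 3.0% for u = 5% and 3.1% × 0.85 = 2.6% for u = 30%.

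**5. A part of the rule that works the other way.** Subjects with an early event are kept, while event-free subjects lost before the window are dropped. Illustration: 5 events among 166 denervation subjects (the arm size in Protocol B.1.2) is 5/166 = 3.0%. If 15% of the 161 event-free subjects are lost (assumed; 161 × 0.15 = 24), the rate becomes 5/142 = 3.5%.

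**The case against.** The strongest reply is that 12-month stenosis has its own analysis. SAP 9.9.2.1 stands apart from the general algorithm, and its precision statement uses 100 subjects in a trial of about 433, which fits a count of imaged subjects better than a count of contacted ones. That reading may well be intended. But the section does not say so, and the only denominator stated anywhere is the contact-based one, which in any case governs the rates in SAP 9.9.2. The separate core-laboratory guidelines and event-committee charter might deal with unresolved scans; they are not part of these documents.

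Second, the number of unscanned subjects may be low. Remote visits are limited to extenuating circumstances, referral to a local imaging center is allowed, and missing data are to be collected at the next possible in-person visit. The German and UK rule aims at a diagnostic scan, so only subjects whose repeats all fail are affected. All of this stands. It bears on how many subjects are affected, not on how they are counted.

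Third, the stenosis analysis at 12 months is descriptive and no success criterion rests on it. That also stands, and is why the point concerns reporting and not the trial's conclusion.

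**Conclusion.** The point holds as a stated counting rule that understates stenosis to the extent that contacted subjects were not scanned. The amount is unknown. The range of 2.9% to 2.2% for a true 3.1% rests on an assumed u of 5% to 30%, equal risk, and no detection without a scan. The 3.1% is itself only an anchor: its cited source is an MRA study, and the figure is not tied to a threshold above 70% or to angiography.

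Several stronger readings are tempting and not supported:
- That the reported rate as a whole can only be too low. Only the missing-scan component has a fixed direction; dropping event-free early losses works upward.
- That stenosis in Germany and the UK cannot be confirmed. The missing angiogram step concerns scans that stay non-diagnostic. The requirement after a positive scan stands in the same bullet of Protocol F.7 and most naturally still applies, although the restriction to ultrasound or MRA leaves some ambiguity.
- That the German and UK path reaches the primary safety endpoint. That endpoint takes stenosis to 6 months, and the 6-month escalation to angiography has no country exception.
- That the 24- and 36-month rates are largely unassessed because imaging there is only catch-up. The rates count events up to the time point, so earlier scans inform them.
- That the prior cohort supplies a value for u, since 78 subjects had office and 71 had 24-hour pressure (SAP Tables 3 and 4). Ambulatory monitoring has its own minimum-readings rule, and these counts say nothing about renal scans.

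**What to change.** In SAP 9.9.2:
1. Keep the planned rows on the planned denominator.
2. Add a separate stenosis row whose denominator is subjects with a diagnostic renal scan for that time point, or a confirmed event. Say which scans count for each time point, including catch-up scans at 24 and 36 months.
3. Report, by group (RDN and control to 6 months; RDN, Crossover and Non-Crossover afterwards) and by visit, the number with no diagnostic scan and the number with a positive scan not resolved by angiography.

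In SAP 9.9.2.1, state that the 12-month rate uses the scanned-subject denominator, and note that being scanned may itself be informative.

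As clarifications only: confirm in Protocol F.7 and the footnotes to Tables 1, 3, 4 and 6 that a positive scan in Germany or the UK leads to angiography. Align Protocol F.10, which puts MRA first for crossover subjects there, with the footnotes to Tables 2 and 5, which allow ultrasound or MRA.

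The cost is one table row and two counts per group and visit, all from data already collected. The added row has a smaller denominator and a wider interval.
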